4.2 Interim analysis

An interim analysis based on the descriptive analysis of the patients included patients and data collected will be produced during the study. This analysis will be performed as soon as 20 CR patients (Cases) are included and have been followed up for six months.

No statistical tests will be performed for this interim analysis.

5 DATA MANAGEMENT CONVENTIONS

5.1 Missing data

Missing data will not be replaced during the data management process and will not be replaced for the statistical analysis, with the exception of the specific cases described in the sections below.

5.2 Derivative data

The following variables will be calculated:

- Interval between visit X and inclusion (in months):
(Date of follow-up visit X - Date of inclusion visit) / 365.25 x 12.
- Total length of follow-up (in months):
(Maximum date between Date of last visit or Date of last news or Date of death - Date of inclusion visit) / 365.25 x 12.
Note: In case of incomplete dates (date of last news or date of death):
If the day is missing, it will be replaced by the first day of the month.
If the month is missing, it will be replaced by the month of January.
If the date completed is earlier than the last visit carried out, then the date will be replaced by the last visit carried out.
- Age (in years):
Year of inclusion – Year of birth.
- Time of diagnosis of metastatic renal cell carcinoma (in years):
(Date of inclusion visit - Date of diagnosis of metastatic renal cell carcinoma) / 365.25.
Note: In case of incomplete dates (date of diagnosis of metastatic renal cell carcinoma):
If the day is missing, it will be replaced by the first day of the month.
If the month is missing, only the year will be used.
- Time from diagnosis of metastatic renal cell carcinoma to nephrectomy (in months):
(Date of nephrectomy - Date of diagnosis of metastatic renal cell carcinoma) / 365.25 x 12
Note: In case of incomplete dates (date of nephrectomy or date of diagnosis of metastatic renal cell carcinoma):
If the day is missing, it will be replaced by the first day of the month.
- Time between diagnosis of metastatic renal cell carcinoma and initiation of Sunitinib (in months):
(Date of Sunitinib initiation - Date of diagnosis of metastatic renal cell carcinoma) / 365.25 x 12
Note: In case of incomplete dates (Sunitinib initiation date or date of diagnosis of metastatic renal cell carcinoma):
If the day is missing, it will be replaced by the first day of the month.

For Cases:

- Time between diagnosis of metastatic renal cell carcinoma and local treatment (in months):
(Date of local treatment - Date of diagnosis of metastatic renal cell carcinoma) / 365.25 x 12
Note: In case of incomplete dates (date of local treatment or date of diagnosis of metastatic renal cell carcinoma):
If the day is missing, it will be replaced by the first day of the month.
-

- Time between Sunitinib initiation and CR (in years):
(Date of CR - Date of Sunitinib initiation) / 365.25.
*Note: In case of incomplete dates (date of CR or date of Sunitinib initiation):
If the day is missing, it will be replaced by the first day of the month.
If the month is missing, only the year will be used.*
- Time between CR and progression (in months):
(Date of progression - Date of CR) / 365.25 x 12
*Note: In case of incomplete dates (date of CR or date of progression):
If the day is missing, it will be replaced by the first day of the month.*
- Progression-free survival (in months):
It is defined as the time between CR and progression or death.
(Date of the event - Date of CR) / 365.25 x 12
Note: Patients who have not progressed and who have not died will be censored at the date of last visit.

Event	Censor decision	Date of the event or censor
Progression	Non-censored	Date of progression
All-cause death without progression	Non-censored	Date of death
Lost to follow-up	Censored	Date of last visit
End of study without progression or death	Censored	Date of last news

For Controls:

- Time between initiation of treatment and progression (in months):
(Date of progression - Date of treatment initiation) / 365.25 x 12
*Note: In case of incomplete dates (date of treatment initiation or date of progression):
If the day is missing, it will be replaced by the first day of the month.*
- Progression-free survival (in months):
It is defined as the time between treatment initiation and progression or death.
(Date of the event - Date of treatment initiation) / 365.25 x 12
Note: Patients who have not progressed and who have not died will be censored at the date of last visit.

Event	Censor decision	Date of the event or censor
Progression	Non-censored	Date of progression
All-cause death without progression	Non-censored	Date of death
Lost to follow-up	Censored	Date of last visit
End of study without progression or death	Censored	Date of last news

- Duration of treatment with Sunitinib (in months):
(Date of treatment discontinuation - Date of treatment initiation + 1) / 365.25 x 12
*Note: In case of incomplete dates (initiation date or discontinuation date):
If the day is missing, it will be replaced by the first day of the month.*

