8.2.3. Inclusion criteria

- Adult patients (≥ 18 years)
- Patients with mRCC confirmed by histological analysis
- Treated with Sunitinib according to a regimen in the text of the SmPC
- Presenting a complete remission in the preceding 5 years (according to RECIST v1.1) with Sunitinib only or combined with localized treatment (surgery, radiotherapy, cryoablation or radiofrequency ablation)
- Patients of childbearing age using a mandatory method of contraception
- Affiliated to a social security scheme
- Informed about the study methods and having given their consent

Exclusion criteria

- Complete remission occurring in the absence of treatment with Sunitinib

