8.2.5.2. Screening of patients

Before any gathering of personal data, the physician will invite the patient to participate in this research and will inform him/her about:

- The objective, the nature of the constraints
- The computer processing of his/her data that will be collected during this research and will also specify his/her rights of access, opposition and rectification of his/her data
- The storage of blood samples for scientific purposes at the end of the research

In addition, during this visit (screening visit), the physician will check the eligibility criteria.

Finally, an information leaflet summarizing these different points will be handed to the patient.

If the patient with metastatic renal cell carcinoma in CR with Sunitinib (Cases) consents to participate in the research, the physician should during the screening visit:

- Obtain his/her express written consent (Appendix 2)
- Complete the screening form and send it, along with the 2 CT scan burnet on 2 CD-ROM, to the IGR.
- Complete the inclusion questionnaire
- Draw 10 ml of blood into 2 EDTA tubes of 5 ml each and send the sample after centrifugation to the IGR
- Collection of a block or in the absence of 15 white slides from a histological sample

If the patient in CR presents disease progression during the 3 years of follow-up:

- Complete the disease progression questionnaire
- Draw 10 ml of blood into 2 EDTA tubes of 5 ml each and send the sample after centrifugation to the IGR
- Collection of a block or in the absence of 15 white slides from a histological sample

If the patient with metastatic renal cell carcinoma without CR with Sunitinib (**Controls**) consents to participate in the research, the physician should:

- Obtain his/her express written consent (Appendix 3)
- Complete the inclusion questionnaire
- Draw 10 ml of blood into 2 EDTA tubes of 5 ml each before starting Sunitinib, at 6 months, at 12 months and during disease progression and send the sample after centrifugation to the IGR.

Receipt and collection of case report forms

The Pfizer project managers will ensure monitoring of incomplete or inconsistent data (checking of inconsistencies, non-responses and omissions) and will be in permanent contact with the physicians.

During the patient screening phase, and based on the number of physicians (no patient enrolled), the project managers will be required to contact these physicians again and remind them about the study deadlines.

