- Visit (Yes/ No);
- Date of visit;
- Best response to treatment received post-progression;
- Duration of administration after progression with first-line Sunitinib;
- Last news: premature discontinuation of study, date of last news, persistent CR since inclusion visit, CR after treatment of post-CR progression, disease progression, number of subsequent lines after progression, post CR;
- Death (Yes/No), date of death.

For Controls

At the 6-month and 12-month follow-up visits of Sunitinib treatment:

- Date of visit;
- Clinical assessment using RECIST criteria (response to treatment, if progression: date of progression, progression at a known metastatic site or at a new site);
- Metastatic sites: location and number of metastatic sites;
- Blood sample and collection date.

If progression:

- Date of visit;
- Date of progression, type of progression (local or distant);
- Metastatic sites: location and number of metastatic sites;
- Blood sample and collection date

At the end-of-research visit (36 months after the inclusion visit):

- Visit (Yes/ No);
- Date of visit;
- Patient still treated with Sunitinib, if yes: response to treatment, if no: progression, new treatment, date of Sunitinib discontinuation;
- Number of subsequent treatment lines;
- Last news: study stopped prematurely, date of last news;
- Death (Yes/No), date of death.

Centralised review of Computerised Tomography Scan (CT Scan) - only for patients in CR

In this research, two of the scans of CR patients (Cases) will be reviewed centrally.

- The scan at initiation of first-line Sunitinib;
- The scan showing CR.

This review will take place between the screening visit and the inclusion visit of the patient. Thus a patient can only be included after the scans have been reviewed to validate the CR.

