3.2 Population of patients included

The patient population included will comprise patients who have signed their consent form and have completed the inclusion visit:

- The Case population will include patients with mRCC in CR (validated after the scan review) taking Sunitinib.
- The Control population will include non-CR patients with mRCC treated with first-line Sunitinib.

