Patient follow-up data will be described for the cases at the end-of-study visit:

- Best objective response observed after progression (Complete / Partial / Progressive / Stabilised);
- Duration of treatment received after progression with first-line Sunitinib (months);
- Early termination of the study (Yes/No);
- Response achieved (persistent CR since inclusion visit / CR after treatment of recurrence / Disease progression);
- Number of subsequent treatment lines from progression, post CR;
- Death (Yes/ No).

Progression-free survival at the end of the study will be analysed using the Kaplan Meier method, with a presentation of the survival curve. The progression-free survival rate will be estimated with a 95% confidence interval.

6.5 Description of follow-up visits for mRCC patients treated with first-line Sunitinib, non CR (Controls)

Study population: Population of followed-up patients - Controls

Patient follow-up data will be described for the controls at 6 and 12 months of treatment:

- Sunitinib dose (50 mg / 37.5 mg / 25 mg);
- Current regimen (4/2 / 2/1 / Continuous);
- Clinical assessment (Complete Response / Partial Response / Stable Disease / Progression);
If Partial Response:
 - Percentage of tumour reduction (%)
- Location of metastases:
 - Lung (Yes/ No);
 - Bones (Yes/No);
 - Liver (Yes/ No);
 - Adrenal glands (Yes/No);
 - Pancreas (Yes/No);
 - Brain (Yes/No);
 - Lymph nodes (Yes / No); If Lymph nodes:
 - Supra-diaphragmatic (Yes/No);

- Sub-diaphragmatic (Yes/No);
- Recurrence at nephrectomy site (Yes/No) ;
- Other (Yes/ No);
A list of the other locations will be presented.
- Number of metastatic sites;

Patient follow-up data will be described for the controls at the time of the progression:

- Time between initiation of treatment and progression (in months);
- Type of progression (Local Progression/Distant Progression);
If distant progression, at which level (at a known metastatic site/new metastatic site);
- Location of metastases:
 - Lung (Yes/ No);
 - Bones (Yes/No);
 - Liver (Yes/ No);
 - Adrenal glands (Yes/No);
 - Pancreas (Yes/No);
 - Brain (Yes/No);
 - Lymph nodes (Yes / No); If Lymph nodes:
 - Supra-diaphragmatic (Yes/No);
 - Sub-diaphragmatic (Yes/No);
 - Recurrence at nephrectomy site (Yes/No) ;
 - Other (Yes/ No);
A list of the other locations will be presented.
- Number of metastatic sites;

Patient follow-up data will be described for the controls at the end-of-study visit:

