Table X - Progression-free survival analysis (months) - Kaplan-Meier

	Total (N=XX)
Progression-free survival (months)	
Number of subjects	99
Event	99 (99.9)
Censored*	99 (99.9)
Min	99.9
Max	99.9
Q3 [95% CI]	99.9 [99.9;99.9]
Median [95% CI]	99.9 [99.9;99.9]
Q1 [95% CI]	99.9 [99.9;99.9]
Mean progression-free survival [95% CI]	99.9 [99.9;99.9]

Name of the SAS programme: P:\XXXXX\XXXXX\Analyse\Pgm\nom_du_programme.sas

Date and time when programme was executed: DDMMYYYY HH:MM

Study: A6181209 - OVERVIEW
Group: XXXXX

Table X – Description of adverse events (AE) by System Organ Class (SOC) and Preferred term (PT)

	Cases (N=XX)		Controls (N=XX)	
	Nb of events	Nb (%) of patients	Nb of events	Nb (%) of patients
At least one adverse event	xx	x (xx.x%)	xx	x (xx.x%)
Body system 1	xx	xx (xx.x%)	xx	xx (xx.x%)
Preferred term 1	xx	xx (xx.x%)	xx	xx (xx.x%)
Preferred term 2	xx	xx (xx.x%)	xx	xx (xx.x%)
...				
Preferred term n	xx	xx (xx.x%)	xx	xx (xx.x%)
Body system 2	xx	xx (xx.x%)	xx	xx (xx.x%)
Preferred term 1	xx	xx (xx.x%)	xx	xx (xx.x%)
Preferred term 2	xx	xx (xx.x%)	xx	xx (xx.x%)
...				
Preferred term n	xx	xx (xx.x%)	xx	xx (xx.x%)
....				
Body system n	xx	xx (xx.x%)	xx	xx (xx.x%)
Preferred term 1	xx	xx (xx.x%)	xx	xx (xx.x%)
Preferred term 2	xx	xx (xx.x%)	xx	xx (xx.x%)
...				
Preferred term n	xx	xx (xx.x%)	xx	xx (xx.x%)

Name of the SAS programme: P:\XXXXX\XXXX\Analyse\Pgm\nom_du_programme.sas

Date and time when programme was executed: DDMMMYYYY HH:MM

Study: A6181209 - OVERVIEW
Group: XXXXX

Table X - Description of adverse events

	Cases (N=XX)	Controls (N=XX)
Qualitative variable		
n	xx	xx
Category 1	xx (xx.x%)	xx (xx.x%)
...
Modality n	xx (xx.x%)	xx (xx.x%)
Missing data	xx	xx
Note: the unit of analysis is the adverse event		

Name of the SAS programme: P:\XXXXX\XXXX\Analyse\Pgm\nom_du_programme.sas
Date and time when programme was executed: DDMMYY HH:MM

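### Case PFS is timed from complete remission by ordinary Kaplan-Meier although cases may enter up to 5 years later, so the curve is biased upward by an amount the documents do not fix

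*SAP*

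**What the plan says.** **Origin and estimator.** SAP 5.2 says of case PFS: "It is defined as the time between CR and progression or death". The formula is event date minus CR date, with no entry-time term. SAP 6.4 states: "Progression-free survival at the end of the study will be analysed using the Kaplan Meier method". Its analysis set is the followed-up cases, who under SAP 3.3 need at least one follow-up visit. The Annex 1 model table reports quartiles, median and mean, each with a confidence interval.

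**Entry.** The case criterion in Protocol 8.2.3 includes: "Presenting a complete remission in the preceding 5 years (according to RECIST v1.1". SAP 3.2 requires a signed consent form and a completed inclusion visit, and SAP 2.3 adds: "Thus a patient can only be included after the scans have been reviewed to validate the CR".

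**Remission at inclusion.** Several places describe cases as still in remission. SAP 3.2 says: "The Case population will include patients with mRCC in CR (validated after the scan review) taking Sunitinib". Protocol 8.2.5.2 treats progression as a later event: "If the patient in CR presents disease progression during the 3 years of follow-up". Protocol 8.1.1 places the screening blood sample during CR. No eligibility criterion, however, requires CR to persist at inclusion. Central review does not test it either: under SAP 2.3, "two of the scans of CR patients (Cases) will be reviewed centrally", namely the scan at the start of Sunitinib and the scan showing CR.

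**Silence.** Neither document mentions delayed entry, left truncation, a landmark, or PFS counted from inclusion.

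**Censoring.** In SAP 5.2 the PFS note censors all event-free patients at the last visit, but the table beneath it censors those who reach the end of study at last news. The same conflict stands in the control block.

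**The concern.** Kaplan-Meier assumes that anyone counted at risk at time t would have been recorded as an event had they failed at t. Between CR and inclusion that is untrue. A death in that interval keeps the patient out of the study, and so may a relapse. Those who do enter bring event-free time that was guaranteed by their entry. Counting it enlarges the early risk sets without the matching events and pushes the curve up.

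The direction follows from the design. Only the size needs assumptions.

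What is at stake is interpretation. Protocol section 6 wants to inform physicians about management after CR, and one of its aims concerns whether patients in CR can discontinue Sunitinib. A PFS curve that starts at CR will be read as duration of remission, and this one would overstate it.

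**Working it through.** **1. The plan's own figures.** The documents give no PFS rate, median or event count. The only design figure is 80% power for Cohen's d of 0.55 with 40 cases and 80 controls. The noncentrality is 0.55 × √(40 × 80 / 120) = 2.84. With 118 degrees of freedom and two-sided 5%, power is 0.804. The figure reproduces, and this point does not touch it.

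**2. Inputs.** From the documents: origin at CR, lag up to 60 months, 36 months of follow-up after inclusion, 40 cases. Assumed, because the documents do not say: PFS from CR, T, is exponential with median 12, 24 or 36 months; the lag L is uniform on 0 to W months and independent of T; no patient is lost before 36 months.

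**3. All cases progression-free at inclusion.** Nobody is censored before month 24, so the planned estimate tends to

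P(T > 24 | T > L) = ∫₀^W S(max(24, l)) dl ÷ ∫₀^W S(l) dl.

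For a median of 24 months and W = 60, λ = ln 2 / 24 = 0.0289. The denominator is (1 − e^(−60λ))/λ = 28.50. The numerator is 24 × 0.5 + (e^(−24λ) − e^(−60λ))/λ = 12 + 11.19 = 23.19. The ratio is 0.81, against a true 0.50.

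| True median (true 24-month PFS) | W = 6 | W = 12 | W = 24 | W = 60 |
|---|---|---|---|---|
| 12 months (25%) | 30% | 35% | 46% | 58% |
| 24 months (50%) | 54% | 59% | 69% | 81% |
| 36 months (63%) | 67% | 71% | 79% | 88% |

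The excess runs from about +4 to +33 points. With a true median of 24 months, the planned method gives medians of 27, 30, 35 and 49 months.

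**4. Relapsed patients admitted less readily** (W = 60, true 50%, deaths ignored). Admitted a quarter as readily: 68%. Half as readily: 60%.

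**5. Relapsed patients admitted freely if alive.** Only survival to inclusion selects, so the estimate is P(T > 24 | T + S > L), where S is post-progression survival, assumed exponential. The true value is 50%.

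| Median S | W = 6 | W = 12 | W = 24 | W = 60 |
|---|---|---|---|---|
| 12 months | 50.4% | 51.6% | 55.5% | 66.6% |
| 24 months | 50.2% | 50.9% | 53.0% | 60.4% |
| 36 months | 50.2% | 50.6% | 52.1% | 57.5% |

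**6. Does a curve from inclusion recover PFS from CR?** Only with a constant hazard. 24-month PFS for W = 60, all cases progression-free at inclusion:

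| Assumed hazard | True, from CR | Planned method | From inclusion |
|---|---|---|---|
| Constant, median 24 | 50% | 81% | 50% |
| Half never relapse, rest median 12 | 62.5% | 91% | 84% |
| Weibull shape 0.6, median 24 | 50% | 87% | 68% |

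**7. Precision with 40 cases** (4,000 simulated studies, W = 60, constant hazard, median 24).
- Planned method: mean 81%.
- Delayed entry from CR: mean 51%, 95% range 15–80%, zero in about 2% of studies. About 4 cases are at risk at month 3 and 12 at month 12.
- Delayed entry from a 12-month landmark, PFS to month 36: mean 50%, range 30–71%.
- From inclusion: mean 50%, range 35–65%.

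**The case against.** **It is a minor, descriptive output.** PFS is in no study objective (SAP 2.2) and not among the endpoints in SAP 2.4. No test uses it. SAP 6.4 also reports case status at 12 and 24 months and whether CR has persisted since inclusion. The mean lag can be recovered, if dates are complete, by subtracting diagnosis-to-Sunitinib and Sunitinib-to-CR from diagnosis-to-inclusion, all planned in SAP 5.2 and 6.3.2. All of this stands and limits the consequence. It does not make the planned curve right.

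**The bias may be negligible.** With short lags, or if relapsed patients entered freely and soon after CR, it may be. The documents do not show which situation applies. The third amendment widened the CR window from 2 to 5 years, so long lags were deliberately allowed.

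**Restarting the clock at inclusion changes the quantity.** This also stands. Delayed entry keeps the SAP's definition. The inclusion-origin curve is more precise but answers a conditional question, and step 6 shows that it too can lie well above PFS from CR.

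**The data for a fix are not all there.** This stands in part. CR and inclusion dates are collected. The case screening and inclusion forms in Protocol Appendix 5 have no field for relapse between CR and inclusion. The case progression form shows a visit date but no progression date, although Protocol 8.1.4 and SAP 2.3 list one.

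**Conclusion.** The concern holds. Followed as written, SAP 5.2 and 6.4 give case PFS estimates that are biased upward. Under the stated assumptions the excess at 24 months runs from about 0 to +33 points. It is large only with long lags and grows with the degree to which relapsed patients were kept out. It should be fixed, but it does not threaten the study's main result.

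A reader might infer four stronger things that the documents do not support:
- **That every case had to be relapse-free at inclusion.** The wording implies it, but no criterion says so, and central review looks only at the baseline and CR scans.
- **That the bias is some particular size, such as +31 points.** Neither the lag distribution nor the relapse rate is given.
- **That the primary comparison is compromised.** It compares patient characteristics and does not use PFS.
- **That a curve from inclusion repairs duration of CR.** It matches PFS from CR only under a constant hazard.

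The censoring conflict is a separate and smaller defect, and it affects both groups.

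**What to change.** In SAP 5.2, 6.4 and 6.5:

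1. Do not present the ordinary CR-origin Kaplan-Meier as duration of CR. Report PFS from the later of inclusion and CR, so that a control switched to the Case group starts at CR. Use included cases (SAP 3.2) who are progression-free at that date, because the followed-up set requires a visit after time zero. Label the curve as conditional on being progression-free at entry. State that it equals PFS from CR only if the hazard is constant, and is higher if the hazard falls.
2. If time from CR is kept, estimate it with delayed entry at inclusion, show numbers at risk, and use a pre-stated landmark where the early risk set is small. Which of the two curves leads is the sponsor's choice.
3. Tabulate the CR-to-inclusion interval and list any case that progressed before inclusion.
4. Separately, for cases and controls, reconcile the PFS note with its table. Censor event-free patients at the last date on which they were known to be progression-free. Count a 36-month visit attended with no progression form on file. The case 36-month form sends only non-attendees to the latest-information form and asks only about response since progression, so attendees could otherwise be cut back to month 24.

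**Cost.** SAP wording and small programming changes. Items 1 and 3 may need a few data queries on relapse before inclusion and on progression dates. The inclusion-origin curve is conditional, and the delayed-entry curve is imprecise with 40 cases.

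### SAP 5.2 gives two conflicting PFS censoring dates for patients who end the study event-free: last visit in the note, last news in the table

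*SAP*

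**What the plan says.** SAP 5.2 defines PFS separately for each group. For Cases, "It is defined as the time between CR and progression or death"; for Controls, "It is defined as the time between treatment initiation and progression or death". Each definition carries the same note: "Patients who have not progressed and who have not died will be censored at the date of last visit".

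Each is followed by the same four-row table, and two of its rows concern censoring:

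- "Lost to follow-up Censored Date of last visit", which agrees with the note;
- "End of study without progression or death Censored Date of last news", which does not.

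The SAP treats last visit and last news as separate dates. Total length of follow-up in 5.2 is built from "Maximum date between Date of last visit or Date of last news or Date of death - Date of inclusion visit".

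On use, SAP 6.4 says "Progression-free survival at the end of the study will be analysed using the Kaplan Meier method", and 6.5 says the same for Controls. Each section asks for a curve and a PFS rate with a 95% confidence interval. The Annex 1 table shell adds the median, quartiles and mean. Neither section plans a test between the groups.

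**The concern.** A patient who ends the study alive and progression-free is covered by both the note and the row "End of study without progression or death". Nothing in the SAP says which governs. If that patient's last news is later than the last visit, the PFS time depends on which line the programmer follows, and two correct implementations could give different curves.

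The choice also has a possible direction. PFS time should stop when disease status was last known. A date of last news need not come with a tumour assessment, so running the clock to that date may credit progression-free time that nobody checked. Kaplan-Meier PFS is the only censored time-to-event analysis in the SAP, and for Cases it describes how long remission lasts.

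**Working it through.** **1. Where the rules differ**

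| Patient without progression or death | Note | Table |
|---|---|---|
| Lost to follow-up | last visit | last visit |
| End of study | last visit | last news |

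The conflict is confined to the second line. The SAP does not define where lost to follow-up ends and end of study begins. A patient with no 36-month visit but with later news could fall in either row.

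**2. When the two dates differ**

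Protocol 8.1.4 D and SAP 2.3 list last news among the items of the 36-month visit, so for a patient who attends that visit the dates should normally coincide. They separate when the visit is missed: the Cases case report form (Protocol Appendix 5) then sends the site to the latest-information or death form.

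The scheduled forms suggest how long a gap could be:

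- Cases have annual follow-up described at 12 and 24 months (SAP 6.4), so a missed 36-month visit leaves 36 − 24 = 12 months.
- Controls have forms at 6 and 12 months, so it leaves up to 36 − 12 = 24 months. Usual-care visits every 2 to 3 months may shorten this.

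**3. What last news contains**

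- Cases: yes/no items on persisting remission and progression, with no scan or dated assessment required (Protocol Appendix 5).
- Controls: premature stop and date only, in SAP 2.3 and in the Controls form (Protocol Appendix 6). Protocol 8.1.4 D also lists progression status, but the form does not carry it.

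**4. Size**

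The documents state no PFS rate, median or dropout share, so there is no figure to reproduce. Everything below is assumed: exponential PFS with median *m*, so S(t) = 2^(−t/m); a share *q*, unrelated to prognosis, last assessed at month 24 with last news at month 36; everyone else followed to month 36.

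*(a) Progression in the gap is never recorded.* Censoring at last visit recovers S(36). Censoring at last news gives

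S(36) + q × [S(24) − S(36)].

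For m = 36: S(24) = 0.630, S(36) = 0.500, difference 0.130. For m = 24: S(24) = 0.500, S(36) = 0.354, difference 0.146.

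| Median | True 36-month PFS | q = 15% | q = 25% | q = 40% |
|---|---|---|---|---|
| 36 months | 50.0% | 51.9% | 53.2% | 55.2% |
| 24 months | 35.4% | 37.6% | 39.0% | 41.2% |

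That is about 2 to 5 points too high at a median of 36 months, and 2 to 6 at 24. If the gap runs from month 12 to month 36, replace S(24) by S(12). With q from 10 to 30% and medians of 12 to 36 months, the excess is about 3 to 11 points. For example, with m = 12 and q = 30%, it is 0.30 × (0.500 − 0.125) = 11.3 points.

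*(b) Progression in the gap is recorded on the progression form.* Last-news censoring now recovers S(36). Last-visit censoring counts those events but removes the event-free gap patients at month 24, and gives

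S(24) × (1 − q) × S(36) / [S(24) − q × S(36)].

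| Median | True 36-month PFS | q = 15% | q = 25% | q = 40% |
|---|---|---|---|---|
| 36 months | 50.0% | 48.2% | 46.8% | 44.0% |
| 24 months | 35.4% | 33.6% | 32.2% | 29.6% |

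*(c) The dates coincide (q = 0).* Both rules give S(36).

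**The case against.** Three arguments count against a stronger claim.

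First, a reader might infer that PFS will be biased upward. The documents do not establish that. Patients are seen every 2 to 3 months in usual care, and Protocol 8.1.4 D and SAP 2.3 provide a progression visit form that is triggered whenever progression occurs. Where that form captures the event, last-news censoring is correct and last-visit censoring is the biased rule, as case (b) shows. This argument stands: the direction depends on whether events in the gap are captured.

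Second, a reader might infer that every event-free patient gets two PFS times, or that all time up to last news is unassessed. Neither follows. Completers should normally have coinciding dates, the lost-to-follow-up row agrees with the note, and last news for Cases carries remission status. The unassessed-time argument has most force for Controls.

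Third, the consequences are limited. PFS is not among the objectives (SAP 2.2) or the endpoints (SAP 2.4), no test is planned, and the sample size does not rest on it. Near a rate of 50%, the 95% half-width before any censoring is 1.96 × √(0.25/40) = 15.5 points for 40 Cases and 1.96 × √(0.25/80) = 11.0 points for 80 Controls. Shifts of 2 to 5 points are small beside that. The 36-month horizon also fits Cases poorly, because their clock starts at a remission that may precede inclusion by up to five years.

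None of this reconciles the note with the table row.

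**Conclusion.** The SAP contradicts itself on the censoring date for patients who end the study event-free, identically for Cases and Controls, and does not say which line governs. This is a matter of text and needs no assumption.

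The numerical effect is conditional. It requires last news to fall after the last visit, and progression in that gap to go unrecorded. Then last-news censoring overstates 36-month PFS by about 2 to 5 points, if 15 to 40% of patients have a 12-month gap and median PFS is 36 months. Those inputs are illustrative. The bias is nil when the dates coincide or when the progression form captures the event.

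The documents do not support calling the planned PFS estimate biased in general, and the case-control comparison and the sample size are untouched. The point should be corrected, but it does not threaten the study's main result.

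**What to change.** In SAP 5.2, put one rule in both notes and both tables: patients alive without progression are censored at the date of the last visit with a documented disease assessment. Replace the date of last news in the end-of-study row, and bring the lost-to-follow-up row to the same wording. The undefined boundary between those two rows then no longer matters. Naming the assessment is needed because a visit alone need not include one. Keep last news for vital status and total length of follow-up.

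The cost is SAP wording only, best settled before the database freeze. There are two downsides. PFS follow-up becomes slightly shorter. There is also some downward bias if progressions after the last assessment are still counted as events while event-free patients are censored earlier, as in case (b). A supplementary curve censored at last news would show how much the choice matters: under the assumptions above, the two curves bracket the truth in both (a) and (b).
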